3.10.3.2 In Clinic Blood Pressure

At each scheduled trial visit, triplicate BP measurements will be performed “in clinic” after 5 minutes of seated rest and with a 1-minute interval between measurements. The last two measurements will be averaged. If only two measures were taken, both will be averaged and if only 1 measure is taken that value will be used.

The baseline value for clinic BP measurement is the value recorded at Week 0. Standing clinic BP measurements will also be summarised descriptively.

Analysis

In clinic BP endpoints listed below:

- Difference in change in clinic SBP from baseline to Week 4,
- Difference in change in clinic DBP from baseline to Week 4,
- Percentage of participants with clinic SBP <140 and DBP <90 mmHg at Week 4,
- Percentage of participants with clinic SBP <130 and DBP <80 mmHg at Week 4
- Percentage of participants with orthostatic hypotension at Week 4
- Percentage of participants with orthostatic hypertension at Week 4

Orthostatic hypotension is defined as a decrease from measured in clinic sitting to standing blood pressure of ≥ 20 mmHg SBP or ≥ 10 mmHg DBP. Orthostatic hypertension is defined as an increase from measured in clinic sitting to standing blood pressure of ≥ 20 mmHg SBP or ≥ 10 mmHg DBP.

Descriptive statistics will be used to summarize secondary endpoints on complete cases only. Continuous endpoints will be summarized using descriptive statistics. Binary endpoints will be summarized with frequency and proportions by treatment groups with exact Clopper Pearson 95% Cis along with associated estimated risk difference, risk ratio and corresponding p-values. Frequency of missing data will be presented. Comparisons will be made between GMRx2 dose levels and Placebo. Exploratory comparisons between GMRx2 dose levels will also be computed.

MMRM will be applied for continuous endpoints using the same approach as the primary endpoint (with no imputations applied). Results will be presented in a similar fashion as home BP. Standing clinic BP measurements will be summarised descriptively by visit. Complete cases analysis will be performed with no imputations for continuous endpoints.

Binary secondary endpoints will be analyzed using GEE regression methods in the same manner as home BP endpoints. Risk differences and 95% CI will be computed for comparisons between GMRx2 dose levels and placebo. Missing values at Week 4 will be imputed as “failures” for the analysis.

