9.2.2. Secondary

- Percentage of participants with an SAE from randomization to Week 4.
- Percentage of participants with symptomatic hypotension from randomization to Week 4.
- Percentage of participants with serum sodium concentration below 135 mmol/l at Week 4.
- Percentage of participants with serum sodium concentration above 145 mmol/l at Week 4.
- Percentage of participants with serum potassium concentration below 3.5 mmol/l at Week 4.
- Percentage of participants with serum potassium concentration above 5.5 mmol/l at Week 4.
- Percentage of participants with serum sodium <135mmol/l or >145 mmol/l, and/or serum potassium <3.5 mmol/l or >5.5mmol/l at week 4.
- Percentage of participants with eGFR drop of over 30% from randomization to Week 4.
- Percentage of participants with postural hypotension at Week 4
- Percentage of participants with postural hypertension at Week 4

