2.5 Sample Size

A total of 250 participants will be randomized: 100 for each of the GMRx2 doses and 50 for placebo group. As noted in Section 12.3 of the protocol, for the comparison of triple $\frac{1}{2}$ vs placebo at week 4, a sample size of 150 participants at a ratio of 2:1 will provide 99.7% power to detect a difference of at least 9 mmHg in mean home SBP, assuming a standard deviation of 11 mmHg. Similarly for the comparison of triple $\frac{1}{2}$ vs placebo at week 4, a sample size of 150 participants at a ratio of 2:1 will provide 100.0% power to detect a difference of at least 13 mmHg in mean home SBP, assuming a standard deviation of 11 mmHg. Therefore, the power for the two comparisons versus placebo will be 99.7% (since $0.997 \times 1.0 = 0.997$). Note that this is a simple, conservative sample size calculation by intention – the actual experimental design and subsequent statistical modelling approach will provide greater power than this.

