2.6 Changes in the Conduct of the Study or Planned Analyses

2.6.1 Changes in the Conduct of the Study

A total sample size of 250 participants was planned; however due to a number of high recruiting centres starting at a similar time towards the end of the study a total of 295 participants were randomized.

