3.3 Multiplicity Adjustment

All tests are to be two-sided with a nominal level of α set at 5%. Since the purpose of the trial is to demonstrate effects on both of the GMRx2 dose versions versus placebo comparisons simultaneously for the designated primary endpoint (i.e., each GMRx2 dose has to be statistically significantly superior at two-sided $p<0.05$ to placebo for the trial to be regarded as positive), there is no need for adjustment of the Type I error for the primary endpoint, according to ICH E9 Guidance and FDA Guidance 'Multiple Endpoints in Clinical Trials. Guidance for Industry, 2022'.

The secondary efficacy parameters measure different aspects of the same underlying treatment effect evaluated in the primary efficacy endpoint, that is the effect of GMRx2 compared to placebo on blood pressure and do not demonstrate additional new treatment effects of the drug, but rather clarify the effect already demonstrated by the primary analysis. No type I error adjustment is proposed to adjust secondary efficacy endpoint analyses.

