endpoint will be the post-Baseline occurrence of the event at Week 4 with fixed effects for treatment group and Baseline home SBP. The variance will be estimated using a sandwich estimator and the model will account for correlation within site. A compound symmetry covariance matrix will account for correlation within site with a fall back of an independent matrix if the model does not converge. The odds ratios and 95% confidence intervals for the occurrence of the events will be estimated for each post-Baseline visit and treatment group. In addition, risk differences and 95% CI will be computed. Pairwise comparisons between GMRx2 doses and placebo will be performed.

Sample SAS Code:

```
PROC GENMOD DATA = ADEFF;
  CLASS SITEID TRTP;
  MODEL AVAL = BASE TRTP / DIST = BIN CL;
  REPEATED / SUBJECT = SITEID TYPE = EXCH;
  WHERE VISIT IN ('WEEK4');
  LSMEANS TRTP / DIFF CL ALPHA=0.05;
  RUN;
```

Risk differences and 95%CI for comparisons between the occurrence of events in GMRx2 dose levels versus Placebo will be computed using the Predictive Margins and Average Marginal Effects SAS Macro (<https://support.sas.com/kb/63/038.html>). Risk differences and 95%CI between GMRx2 dose levels will also be computed. Sample SAS code with implementation to simulated data is provided in Appendix 3.

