3.11.2 Laboratory Parameters: Hematology, Biochemistry & Urine

Blood hematology, biochemistry and urine parameters will be collected according to the schedule of events. Only scheduled visit results will be presented in summary tabulations. Unscheduled visits will be included in data listings only. The baseline value for each parameter will be the latest non-missing value recorded before randomization (i.e., prior to Period 2).

Estimated Glomerular Filtration Rate (eGFR) results provided by the various pathology laboratories across study may be calculated by different equations; however any differences are expected to be balanced across randomized treatment groups and no adjustments will be made.

Actual values and changes from baseline for all laboratory parameters will be descriptively summarized by treatment group. A subset by-participant listing of out-of-range values will be presented.

In addition, tabular descriptive summaries will present the number and percentage of participants at Week 4 with:

- serum sodium concentration below 135 mmol/l
- serum sodium concentration above 145 mmol/l

- serum potassium concentration below 3.5 mmol/l
- serum potassium concentration above 5.5 mmol/l
- serum sodium <135mmol/l or >145 mmol/l, and/or serum potassium <3.5 mmol/l or >5.5mmol/l at week 4
- eGFR (estimated GFR) drop of over 30% from baseline

Frequencies and proportions, including frequency of missing data will be presented. Risk differences with 95% CI, computed using the Newcombe hybrid score method (with continuity correction), to evaluate GMRx2 dose levels against Placebo will be performed. The analysis of binary secondary safety endpoints will be performed on the Safety Analysis Set, limited to those participants who were randomized. Participants will be grouped as treated.

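### The logistic GEE planned for orthostatic hypotension and hypertension gives no usable odds ratio, and can give too narrow a risk-difference interval, if an arm has no events; the fallback does not cure this.

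*SAP*

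**What the plan says.** Protocol 9.2.2 lists "Percentage of participants with postural hypotension at Week 4", and the matching hypertension item, as secondary safety outcomes. SAP 2.4.2.2 does the same.

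The analysis, however, is placed in SAP 3.10.3.2, within the secondary efficacy section. "Percentage of participants with orthostatic hypotension at Week 4" stands there beside the clinic BP-control percentages, followed by the rule "Binary secondary endpoints will be analyzed using GEE regression methods in the same manner as home BP endpoints". The home BP method in SAP 3.10.3.1 is a binomial GEE on the Randomized Set, with baseline and treatment as terms and clustering by site. The sample code names no link, so the default logit applies. It reports odds ratios, plus risk differences from a margins macro. The one contingency is a compound symmetry matrix "with a fall back of an independent matrix if the model does not converge". Missing Week 4 values count as failures.

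SAP 3.10.3.2 also plans a complete-case summary: frequencies, Clopper-Pearson limits per arm, and a risk difference, risk ratio and p-values.

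For sodium, potassium and eGFR, SAP 3.11.2 plans "Risk differences with 95% CI, computed using the Newcombe hybrid score method (with continuity correction), to evaluate GMRx2 dose levels against Placebo". It places binary secondary safety endpoints on the Safety Set (randomized participants, as treated), but its list omits the two orthostatic endpoints. SAP 3.11.1.2 uses the same Newcombe method for adverse events.

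**The concern.** A logistic model cannot give a finite log-odds for an arm in which nobody has the event. Placebo is the smallest arm, so it is the likeliest to be empty. If it is, both dose-versus-placebo odds ratios fail together. If a dose arm is empty, only the contrasts with that dose fail.

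The fallback changes the working correlation, while the trouble is the empty cell. Its trigger is non-convergence, so a fit that drifts to a huge coefficient and then reports convergence passes unnoticed.

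What is at stake is a safety comparison in the pattern that matters most: no events on placebo and some on GMRx2. The plan would then print an unusable odds ratio beside a risk difference that looks more precise than the data allow.

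A second problem does not depend on the event rate. SAP 3.10.3.1 and SAP 3.11.2 point these endpoints to different analysis sets. Failure also has no obvious direction when the endpoint is a harm.

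**Working it through.** **Inputs.** SAP 2.5: "A total of 250 participants will be randomized: 100 for each of the GMRx2 doses and 50 for placebo group". SAP 2.6.1: "a total of 295 participants were randomized". A 2:2:1 split of 295 gives 118, 118 and 59; that split is an assumption. Protocol section 4 gives about 25-30 sites, and 27 was used in simulation. The documents state no orthostatic event rate, so there is no figure of theirs to reproduce on this point.

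**Step 1: chance of an empty arm.** For one arm this is (1 - p)^n. For any of three arms with a common rate it is 1 - [1 - (1-p)^59] × [1 - (1-p)^118]². The rates are assumed.

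| True rate p | Placebo empty, n = 50 | Placebo empty, n = 59 | Any arm empty, 59/118/118 |
|---|---|---|---|
| 1% | 60.5% | 55.3% | 78.4% |
| 2% | 36.4% | 30.4% | 42.6% |
| 3% | 21.8% | 16.6% | 21.1% |
| 5% | 7.7% | 4.8% | 5.3% |
| 8% | 1.5% | 0.7% | 0.7% |
| 10% | 0.5% | 0.2% | 0.2% |

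**Step 2: the estimating equation under independence.** With 0/50 on placebo and baseline held at its mean, the placebo contribution is -50 × expit(intercept). It is -0.90 at an intercept of -4, -0.0168 at -8 and about -1.0e-7 at -20. It approaches zero without reaching it, so no finite root exists.

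**Step 3: the specified GEE on simulated data.** Baseline plus treatment, 27 sites, 300 data sets per scenario, fitted in Python (statsmodels). A fit counted as finite if it converged with every coefficient below 10 in absolute value.

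| Events (dose 1, dose 2, placebo) | Exchangeable: finite fits | Independence: finite fits |
|---|---|---|
| 4/100, 5/100, 0/50 | 0 of 300 | 0 of 300 |
| 5/118, 6/118, 0/59 | 0 of 300 | 0 of 300 |
| 0/100, 5/100, 3/50 | 0 of 300 | 0 of 300 |
| 4/100, 5/100, 2/50 (control) | 300 of 300 | 300 of 300 |

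In the first scenario the exchangeable fits split into 154 with very large coefficients and 146 undefined or in error; all 300 independence fits had very large coefficients. Individual independence fits were reported as converged. One had a dose 1 versus placebo log odds ratio of 23.3 with an undefined standard error. Another, with no events on dose 1, had -23.8 with a standard error of 0.54.

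**Step 4: the risk difference.** Take 5/118 against 0/59, a difference of 4.24%.

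- *Wald-type interval.* The empty arm adds no variance, so SE = √(0.0424 × 0.9576 / 118) = 1.85%. The interval is 4.24% ± 1.96 × 1.85%, or about 0.6% to 7.9%, which excludes zero. This ignores site clustering.
- *Newcombe with continuity correction.* The single-arm score limits are 1.57% to 10.10% for 5/118 and 0 to 7.62% for 0/59. Lower limit: 4.24 - √[(4.24 - 1.57)² + 7.62²] = 4.24 - 8.07 = -3.8%. Upper limit: 4.24 + (10.10 - 4.24) = 10.1%.
- Fisher's exact p = 0.17.

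With site clustering, one simulated 4/100 against 0/50 data set (treatment-only model, independence, site sandwich) gave 4.0% (0.4% to 7.6%). Newcombe gives -5.3% to 10.5%, and Fisher's p is 0.30.

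**Step 5: what the other planned summary gives.** With 0/59 the Clopper-Pearson upper limit is 6.1%, so the placebo arm is still described. The raw risk difference exists, but no interval method is named for it. The risk ratio divides by zero.

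**Step 6: the texts side by side.** SAP 3.10.3.1 runs the GEE on the Randomized Set, as randomized. SAP 3.11.2 puts binary secondary safety endpoints on the Safety Set, as treated. SAP 3.10.1.2 treats a missing binary value as endpoint not achieved, which for a harm means no event and leaves an empty arm empty. Reading failure as the bad outcome would instead turn each missing value into an imputed event.

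**The case against.** The strongest reply is that the comparison does not rest on the GEE alone. The complete-case summary is prespecified and would report counts, exact limits per arm and a raw risk difference whatever the GEE does. That stands. A reader might infer that an empty arm would leave these endpoints with no reportable result, or that a whole replacement analysis would have to be chosen after unblinding. The documents do not support either inference. What stays open is the interval method for the raw difference, and the lack of any rule saying that the summary replaces a failed GEE.

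Second, SAP 3.10.1.2 plans no hypothesis tests for secondary endpoints and calls the results exploratory. Symptomatic hypotension is collected as an adverse event of special interest and already gets the Newcombe interval. Both facts lower the stakes. They do not make a falsely narrow interval acceptable.

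Third, the rate may be too high for the problem to arise. The definition is broad (20 mmHg systolic or 10 mmHg diastolic), and Protocol Appendix 2 takes one standing reading. If sit-to-stand diastolic change were centred at zero with an SD of 6 to 8 mmHg (an assumption), the diastolic limb alone would give about 5% to 11% in each direction, and an empty placebo arm would have a chance of about 5% down to 0.1%. This is fair: 30% is the figure at an assumed 2%, not a forecast.

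Fourth, Protocol 12.4 itself sends binary safety outcomes to the GEE. That is so, but SAP 3.11 already uses Newcombe intervals for the adverse event and laboratory comparisons.

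**Conclusion.** The point holds, conditionally on an arm having no events, and it is minor. In that case the odds ratios against the empty arm are not estimable, the independence fallback does not cure this and may report convergence, and the model-based risk difference can be falsely precise.

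A reader might infer that the risk difference is also not estimable. It is finite; its interval is the problem.

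The size depends on an unknown rate. The chance of an empty placebo arm of 59 runs from 55% at 1% to under 1% at 8% or more. The failure is exact under independence. Under the exchangeable matrix it is shown by simulation (0 of 900 finite fits over three scenarios), and the planned SAS procedure may report convergence differently from the software used here. The conflict over analysis set and the unclear direction of failure hold at any rate.

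**What to change.** Before unblinding, move both orthostatic endpoints to SAP 3.11 and analyse them as the other binary safety endpoints: randomized participants in the Safety Set, as treated; observed data with the number missing shown by arm; and the Newcombe hybrid-score risk difference with 95% CI for each dose against placebo. Limit the GEE and the failure imputation to the BP-control endpoints.

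The cost is about one paragraph, with no new method and no new data. These two exploratory endpoints would lose adjustment for site and baseline. SAP 2.6.2 mentions expanded methods for secondary safety endpoints only in general terms, so it should record the departure from the GEE in Protocol 12.4. A prespecified penalised or exact method for an arm with no or few events would also cure the empty-cell problem, but the analysis set and missing-data rule would still need settling.

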2.4.2.2 Secondary

- Percentage of participants with an SAE from randomization to Week 4.

- Percentage of participants with symptomatic hypotension from randomization to Week 4.
- Percentage of participants with serum sodium concentration below 135 mmol/l at Week 4
- Percentage of participants with serum sodium concentration above 145 mmol/l at Week 4
- Percentage of participants with serum potassium concentration below 3.5 mmol/l at Week 4
- Percentage of participants with serum potassium concentration above 5.5 mmol/l at Week 4
- Percentage of participants with serum sodium <135mmol/l or >145 mmol/l, and/or serum potassium <3.5 mmol/l or >5.5mmol/l at Week 4.
- Percentage of participants with eGFR drop of over 30% from randomization to Week 4
- Percentage of participants with orthostatic (postural) hypotension at Week 4
- Percentage of participants with orthostatic (postural) hypertension at Week 4

In addition, descriptive safety data will be reported on:

- Percentage of participants discontinued trial medication due to AE/SAE during the placebo run-in period.
- All AESI and SAEs, by severity and by System Organ Class (SOC) criteria during the run-in period, by trial medication group during the randomized treatment period and safety follow-up period or Open-Label Extension Period.

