3.10.1.2 Secondary Estimand

The population for the secondary estimands includes adults (aged ≥ 18 years) with hypertension. The variables of interest are listed in Section 2.4.1.2.

Hypothesis testing is not planned for secondary endpoints and, therefore, the results of the planned analyses are considered exploratory. Statistical analyses for continuous secondary endpoints will be performed on Complete Cases only. Statistical analyses for binary secondary endpoints will be performed on the Randomized Set, where participants with missing endpoint values will be assumed to have not achieved the endpoint (i.e., missing data will be singly imputed as "failure").

Table 3-1 Estimands

Estimand Label	Treatment Comparison	Population	Population-level summary	Analysis Population	Handling of Intercurrent events
Primary Analysis	GMRx2-dose 1 vs Placebo and GMRx2-dose 2 vs Placebo at week 4	Adults with hypertension	Difference in change in home SBP, for GMRx2 vs Placebo Analysis will be performed using MMRM with Multiple Imputation	Randomized Set	Treatment policy strategy with intercurrent events only used as part of missing data imputation strategy
Primary Estimand, Sensitivity Analysis – Adjusted Analysis	GMRx2-dose 1 vs Placebo and GMRx2-dose 2 vs Placebo at week 4	Adults with hypertension	Difference in change in home SBP, for GMRx2 vs Placebo Analysis will be performed using MMRM with Multiple Imputation, adjusted for covariates	Randomized Set	Treatment policy strategy with intercurrent events only used as part of missing data imputation strategy
Primary Estimand, Sensitivity Analysis – Adjusted Analysis	GMRx2-dose 1 vs Placebo and GMRx2-dose 2 vs Placebo at week 4	Adults with hypertension	Difference in change in home SBP, for GMRx2 vs Placebo Analysis will be performed using MMRM with Multiple Imputation, with interaction terms for specified subgroups	Randomized Set	Treatment policy strategy with intercurrent events only used as part of missing data imputation strategy
Primary Estimand, Supplemental Analysis	GMRx2-dose 1 vs Placebo and GMRx2-dose 2 vs Placebo at week 4	Adults with hypertension	Difference in change in home SBP, for GMRx2 vs Placebo Analysis will be performed using MMRM with Multiple Imputation	Full Analysis Set	Treatment policy strategy with intercurrent events only used as part of missing data imputation strategy

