separately for those with intercurrent events and those without
intercurrent events. Note also that baseline values will be imputed from
all observations.;

PROC MIXED DATA = ADEFF EMPIRICAL METHOD = REML;
  BY IMPUTNUM;
  CLASS SITEID TRTP;
  MODEL AVAL = BASE TRTP / CL;
  REPEATED / SUBJECT = SITEID TYPE = CS;
  WHERE VISIT IN ('WEEK4');
  LSMEANS TRTP / DIFF CL ALPHA=0.05;
  ODS OUTPUT COVPARMS = CP LSMEANS = LSM DIFF = DIFFS;
  RUN;
PROC SORT DATA = DIFF;
  BY TRTP _TRTP;
  RUN;
PROC MIANALYZE DATA = DIFF ALPHA = 0.05;
  BY TRTP _TRTP;
  WHERE TRTP NE 3 AND _TRTP = 3;
  *TRTP = 3 corresponds to placebo in this example;
  MODELEFFECTS ESTIMATE;
  STDERR STDERR;
  ODS OUTPUT PARAMETERESTIMATES=SBP_PROP;
  RUN;
```

TRTPN is the planned treatment group, SEX is the sex of the participant, RACE is participant race, ETHNIC is participant ethnicity, SMK is participant smoking status, ALC is alcohol use. BASE is the baseline (at Randomization) average SBP value and SBP4 is the average SBP value at FU1/Week 4. The minimum and maximum values for SBP imputation may be modified according to the observed minimum and maximum within the sample. If the multiple imputation models cannot converge, model reduction (excluding covariates) may be performed.

For binary endpoints with missing results, a single value imputation of “failure” will be performed for analysis ([Section 3.10.1.2](#)).

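### SAP 3.10.3.2 applies the efficacy rule that a missing value is a failure to two safety endpoints, orthostatic hypotension and hypertension, without defining failure for a harm

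*SAP*

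**What the plan says.** Protocol 9.2.2 and SAP 2.4.2.2 both place postural hypotension and postural hypertension among the secondary safety outcomes; the SAP entry for the first reads "Percentage of participants with orthostatic (postural) hypotension at Week 4". Neither condition is in the secondary efficacy list (Protocol 9.1.2, SAP 2.4.1.2).

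SAP 3.10.3.2 nevertheless lists both with the clinic blood pressure endpoints, under the general heading for secondary efficacy analyses (for example "Percentage of participants with orthostatic hypotension at Week 4"). It then gives two analyses for the binary endpoints in that list:

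- A summary without imputation: "Descriptive statistics will be used to summarize secondary endpoints on complete cases only". For binary endpoints this includes exact intervals, risk differences, risk ratios, p-values and the frequency of missing data.
- A regression: "Binary secondary endpoints will be analyzed using GEE regression methods in the same manner as home BP endpoints". The section ends with "Missing values at Week 4 will be imputed as" failures, and no endpoint is exempted.

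The meaning of failure is given elsewhere. SAP 3.10.1.2 says that "participants with missing endpoint values will be assumed to have not achieved the endpoint". SAP 3.10.2.6 restates the rule in general terms ("For binary endpoints with missing results, a single value imputation of" failure) and refers back to 3.10.1.2. The home blood pressure model that the clinic GEE copies (SAP 3.10.3.1) states that the "endpoint will be the post-Baseline occurrence of the event at Week 4".

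**The concern.** For a blood pressure target, treating a missing participant as not controlled is a familiar cautious choice: it cannot make an arm look better than its observed data. That reasoning does not carry over to a harm. If missing means that the endpoint did not occur, each missing participant lowers the reported harm rate. If missing means the bad outcome, each one is counted as having had both orthostatic hypotension and orthostatic hypertension. Either way, a participant with no data is given a fixed harm status.

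The group affected is wider than those who miss the Week 4 visit. Both conditions compare seated with standing pressure, and Protocol Appendix 2 provides one single standing reading per visit. Someone who attends with seated values but no standing value is missing for both endpoints.

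What is at stake is a clear reading of a plausible harm of a blood-pressure-lowering combination; Protocol 5.7 itself expects that dizziness and hypotension may increase. There is also a grouping conflict. The GEE runs on the Randomized Set, grouped as randomized (SAP 3.4.3, 3.10.3.1), while SAP 3.4.2 requires safety endpoints to be analysed by treatment actually received.

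**Working it through.** **What the text implies.** The plan has no figure of its own to reproduce here: neither document gives an orthostatic event rate or a missing-data rate. The first step is therefore textual.

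1. SAP 3.10.3.2 sends all its binary endpoints to GEE and imputes missing values as failures.
2. The only explanation of failure (3.10.1.2) is that the endpoint was not achieved.
3. The modelled outcome (3.10.3.1) is occurrence of the event at Week 4.
4. For an endpoint defined as having orthostatic hypotension, steps 1 to 3 code a missing participant as having no event. This is the literal coding.
5. However, 3.10.1.2 takes its variables from the efficacy list in 2.4.1.2, which contains no orthostatic endpoint. For these two endpoints failure is undefined, and a programmer could code it as the harm having occurred. Call this the bad-outcome coding.

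**Formulas.** Let p be the event rate among observed participants and m the missing proportion, with A for active and P for placebo.

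- Complete-case rate: p
- Literal rate: (1 − m)p
- Bad-outcome rate: (1 − m)p + m
- Literal minus complete-case risk difference: mP·pP − mA·pA
- Bad-outcome minus literal risk difference: mA − mP

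If every m and p is 10% or less, the literal shift is at most 0.10 × 0.10 = 1.0 point.

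**Assumed rates: 10% active, 5% placebo.** The complete-case risk difference (RD) is 5.0 points and the risk ratio (RR) 2.00.

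| Missing, active / placebo | Literal RD (RR) | Bad-outcome RD (RR) |
|---|---|---|
| 2% / 2% | 9.8 − 4.9 = 4.9 (2.00) | 11.8 − 6.9 = 4.9 (1.71) |
| 5% / 5% | 9.5 − 4.75 = 4.75 (2.00) | 14.5 − 9.75 = 4.75 (1.49) |
| 10% / 10% | 9.0 − 4.5 = 4.5 (2.00) | 19.0 − 14.5 = 4.5 (1.31) |
| 5% / 2% | 9.5 − 4.9 = 4.6 (1.94) | 14.5 − 6.9 = 7.6 (2.10) |
| 15% / 5% | 8.5 − 4.75 = 3.75 (1.79) | 23.5 − 9.75 = 13.75 (2.41) |
| 5% / 10% | 9.5 − 4.5 = 5.0 (2.11) | 14.5 − 14.5 = 0.0 (1.00) |

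With equal missingness both codings shrink the risk difference by the missing proportion, and the literal coding leaves the risk ratio unchanged. With more missing data on active, the two codings fall on opposite sides of the complete-case result.

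**Whole-number check.** SAP 2.6.1 reports 295 randomized. Assume a 2:2:1 split: 118 per dose and 59 on placebo. Intervals are 95% Newcombe with continuity correction.

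- Equal missingness (6/118 and 3/59, 5.1% each), 11/112 versus 3/56 events. Complete cases: +4.5 points (−6.9 to 12.9). Literal, 11/118 versus 3/59: +4.2 (−6.6 to 12.3). Bad outcome, 17/118 versus 6/59: +4.2 (−8.4 to 14.2).
- Unequal missingness (6/118 and 1/59, 5.1% and 1.7%), 11/112 versus 3/58 events. Complete cases: +4.6 (−6.5 to 13.0). Literal, 11/118 versus 3/59: +4.2 (−6.6 to 12.3). Bad outcome, 17/118 versus 4/59: +7.6 (−4.2 to 16.8).

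Every interval includes zero. These are crude proportions; the GEE also adjusts for baseline home SBP and site clustering, so its estimates would not match exactly.

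**Grouping.** Run-in dosing counts towards the Safety Set (SAP 3.4.2), so membership is essentially the same as the Randomized Set. Only participants given the wrong treatment, or never dosed after randomization, would be grouped differently. One such participant is 1/59 = 1.7 points of the placebo denominator or 1/118 = 0.8 points of a dose arm.

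**The case against.** The strongest reply is that 3.10.3.2 already plans an analysis without imputation for these same endpoints, with risk differences, risk ratios, p-values and missing counts. The GEE is additional, and no missing participant is hidden. Symptomatic hypotension is a separate safety outcome, collected as an adverse event of special interest, and is untouched by this rule. Using GEE is also consistent with Protocol 12.4, which sends other binary outcomes, safety included, to the same method. All of this stands, and it keeps the point modest. It does not settle which of two risk differences for the same harm is the reported one, or what failure means in the second.

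A reader might infer that the SAP definitely counts missing participants as free of the harm. The documents do not go that far: that is the literal reading, but the defining section covers only the efficacy list, and 3.10.3.2 does not define the word for a harm.

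A reader might also infer, from the general sentence in 3.10.2.6, that the laboratory safety endpoints are imputed in the same way. That is not supported. The sentence sits in the primary efficacy missing-data section and refers back to 3.10.1.2, while 3.11.2 sets its own method for the laboratory endpoints, reports missing counts and states no imputation.

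On grouping, Protocol 12.4 opens by placing all analyses on an intention-to-treat basis. Grouping by treatment received follows SAP 3.4.2 but departs from that sentence, so the two need to be reconciled openly. The number of participants affected is not given and may be zero.

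**Conclusion.** The point holds as a misapplied rule of undefined direction. An imputation rule written for blood pressure control reaches two endpoints that both documents class as safety, and either coding gives every missing participant a fixed harm status without justification.

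The size is modest. Under the literal coding the risk difference moves by no more than 1.0 point when event and missing rates are 10% or less. The larger movements in the table (for example 7.6 points against 5.0) need the bad-outcome coding together with unequal missingness. All event and missing rates are assumptions, so none of these figures predicts what the trial will show, and nothing here touches the primary endpoint. The wording should be corrected because the correction is cheap and the programming is otherwise open to two opposite codings.

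**What to change.** In the SAP:

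- In 3.10.3.2, limit the imputation sentence to the two clinic control endpoints (<140/90 and <130/80 mmHg).
- In 3.10.2.6, limit the general sentence to the four blood pressure control endpoints in 2.4.1.2. Section 3.10.1.2 needs no change, since it already covers only that list.
- In 3.10.3.2, state that orthostatic hypotension and orthostatic hypertension are analysed on observed Week 4 data (seated and standing values both present), with the number missing shown by arm.
- Name the complete-case risk difference already planned there as the reported result for these two endpoints. Any GEE kept for agreement with Protocol 12.4 runs without imputation.
- Group these two endpoints by treatment received, as SAP 3.4.2 requires for safety endpoints, and record this as an exception to the intention-to-treat sentence in Protocol 12.4.

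The cost is a few sentences of SAP wording. No new data or new analysis is needed.
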